The study protocol follows the requirements of the standard ISO 80601-2-61:2017 "Medical electrical equipment - Part 2-61: particular requirements for basic safety and essential performance of pulse oximeter equipment". As such, in this study BrOxy M and the reference device will be tested on healthy volunteers accepting to participate in a controlled desaturation study. Use of both devices will be in accordance with the limitations imposed by and instructions included in the BrOxy M and Reference device User Manual.

Due to the use of a controlled desaturation protocol foreseen by the standard ISO 80601-2-61:2017, this study is classified as an interventional post-market clinical study in accordance with Annex I of EN ISO 14155:2020.

Clinical Investigational Plan		
Protocol No.:	Version 1.0	Page 15 of 45
01M2020-CH.LMD	Date: 22 December 2020	

During the execution of the protocol, the following measurements will be acquired in continuous mode:

- 1) the SpO₂ and HR values from the reference device, and
- 2) the photoplethysmographic signals with BrOxy M.

As shown in Figure 1, the protocol provides for the maintenance of 4 plateaus at 4 different values of saturation in steps of 5% and, therefore, at 97%, 92%, 87% and 82% SpO_2 . The SpO_2 value displayed on the reference device will be used to check the saturation level reached during each plateau level. For each level, at least 30" will be expected in order to stabilize the SpO_2 value and, subsequently, the plateau will be maintained for 2.5', continuing the parallel acquisition with both the reference device and BrOxy M.

[figure not shown]

Figure 1: Time distribution of the SpO₂ measurements to be carried out on each individual subject.

Four different saturation plateaus will be used, waiting for the plateau stabilization before starting the 2.5' signal recording from which the series of 8 measurements with at least 20' of pause are extracted by means of a post-processing algorithm.

After data acquisition, up to 8 measurements for SpO₂ and HR will be selected from each plateau as follows:

- Reference device: SpO₂ and HR values will be selected starting from at least 30" after plateau stabilization, with a time interval between measurements of at least 20".
- BrOxy M: SpO₂ and HR values generated by BrOxy M will be obtained by processing the
 photoplethysmographic signals generated by the device with the BrOxy Medical software. Then,

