7.2 ENDPOINTS

The **primary endpoint** of the study will be a comparison of the accuracy of SpO_2 and HR measurements obtained with BrOxy M with that obtained with the reference pulse oximeter in paired observations over a range between 80% and 100% SpO_2 .

For each subject, four different saturation plateaus will be set up (i.e. at 97%, 92%, 87% and 82% SpO_2), waiting 30" before starting to keep the SpO_2 level on each plateau for 2.5' in order to obtain 8 measurements in post-processing. These measurements will be at least 20" away from each other, for a total of 32 measurements for each subject, as summarized in Table 1.

The study will follow the procedures described in the standard ISO 80601-2-61:2017 "Medical electrical equipment - Part 2-61: particular requirements for basic safety and essential performance of pulse oximeter equipment".

As **secondary endpoints**, the following will be verified:

• whether any relation exists between the accuracy of BrOxy M for both SpO₂ and HR and subject skin pigmentations as measured with the Fitzpatrick scale.

Clinical Investigational Plan			
Protocol No.:	Version 1.0	Page 22 of 45	
01M2020-CH.LMD	Date: 22 December 2020	1.80 == 0. 10	

• that no adverse events related to the use of BrOxy M, besides a temporary slight skin irritation of the wrist, will occur.

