8.2 RISKS

Each subject enrolled in the study will be exposed to experimentally generated, controlled hypoxia, starting from $97\% O_2$ and reaching $83\% O_2$ as the lowest level. During the desaturation protocol, which is expected to last a maximum of 35 minutes for each subject, SpO_2 and cardiac frequency will be measured continuously using BrOxy M and the reference device.

The following considerations were made about the potential risks that subjects enrolled in this study will be exposed to:

- Risks associated to the use of BrOxy M and the reference device are negligible, i.e. for BrOxy M a slight irritation of the skin where the bracelet is placed can sometimes be expected. For the reference device subjects may exhibit allergic reactions to the adhesive tape. For this reason subjects with known allergy to adhesive tapes should be excluded from the study
- The absence of pre-existing cardiovascular or pulmonary disease that may expose subjects to increased risks when participating in the study will be carefully checked at screening (see exclusion criteria in Section 10.2)

It is expected that, due to the use of a controlled desaturation protocol foreseen by the standard ISO 80601-2-61:2017, this study is classified as an interventional post-market clinical study in accordance with Annex I of EN ISO 14155:2020.

- Values may be below 90% for a maximum continuous period of 3 minutes. The Principal Investigator will be equipped with a chronograph with a timer and alarm function to avoid exposure of the subjects to longer periods of hypoxia.
- The lowest SpO₂ that subjects will be exposed to is 82% for maximum 3 minutes (30" for stabilization and 2.5' for signal recording). This situation is similar to the one that a subject would have by staying at an altitude of around 3,500-4,000 meters for 3 minutes. Data in literature indicate that there are no risks for healthy subjects for permanence time below 30 minutes at altitudes up to 5,500 m (32).
- The full test will be performed only once on each subject.
- The study will be performed in an outpatient pneumology department, where medical assistance can be promptly provided if necessary.

Clinical Investigational Plan			
Protocol No.:	Version 1.0	Page 23 of 45	
01M2020-CH.LMD	Date: 22 December 2020	.0-	

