11.2 VISIT 1 – TEST SESSION (DAY 1)

The study involves, starting from medical air (O2 concentration 20.98%), the subsequent use of cylinders with an oxygen concentration of 15%, 13% and 11%, rest nitrogen. We will use a Hans Rudolph one-way valve connected to the subject with a nose piece to eliminate nasal ventilation and with a disposable mouthpiece and filter. The valve on the inhalation side will be connected, with a two-way tap, to a Douglas bag supplied by the gas cylinder with a concentration selected according to the target level of SpO_2 to be obtained (see Table 1).

From each session of measurements on each subject, the photoplethysmographic signals in the red and infrared frequency will be collected from the subject's wrist, while the comparison measurements will be carried out using the reference oximeter.

As shown in Figure 1, during the execution of the protocol, four different saturation plateaus will be used (in steps of 5% and, therefore, at 97%, 92%, 87% and 82%), waiting 30" before starting to keep the SpO₂ level on each plateau for 2.5' in order to obtain 8 measurements in post-processing. These measurements will be at least 20" away from each other, for a total of 32 measurements for each subject as summarized in Table 1 (on page 17 and replicated below).

Plateau no.	Range SpO₂ (%)	Inhaled solution	Plateau duration	N. of Measurements of SpO ₂ and HR extracted from recordings
1)	95 – 100 (target 97%)	Ambient air (medical air)	2.5'	8
II)	90 – 94 (target 92%)	O2 15% + N 85%	2.5'	8
III)	85 – 89 (target 87%)	O2 13% + N 87%	2.5'	8
IV)	80 – 84 (target 82%)	O2 11% +N 89%	2.5'	8
			Total	32 measurements

Clinical Investigational Plan			
Protocol No.:	Version 1.0	Page 28 of 45	
01M2020-CH.LMD	Date: 22 December 2020	rage 28 01 43	

Table 1: Number of measurements to be performed for each subject, for each target level of SpO₂ and indication of the gaseous solution inhaled during each target level.

[figure not shown]

Figure 1: Time distribution of the SpO_2 measurements to be carried out on each individual subject. Four different saturation plateaus will be used, waiting the plateau stabilization before starting the 2.5' signal recording from which the series of 8 measurements with at least 20' of pause are extracted by means of a post-processing algorithm.

Before starting the measurement protocol, as shown in Figure 1, in order to prepare the above instrumentation, it is necessary to carry out the following operations:

- 1. Start the PC;

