At this point, once all the above conditions are verified, the values of SpO_2 and HR are calculated for the signal windows considered. These values are considered acceptable if the following conditions occur at the same time:

- Heart rate values between 40 and 280 bpm
- SpO₂ values between 80 and 100 %

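### Section 8.2's exposure limits contradict each other and the test schedule: two different lowest SpO₂ values, both above the plateau IV floor, and a 3-minute maximum built from a stabilisation time that Section 3 makes a minimum

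*Combined protocol and SAP*

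**What the plan says.** **Lowest level.** The opening sentence of Section 8.2 describes controlled hypoxia starting from 97% and "reaching $83\% O_2$ as the lowest level". A later bullet in the same section says: "The lowest SpO₂ that subjects will be exposed to is 82% for maximum 3 minutes (30' for stabilization and 2.5' for signal recording". The 30 in that bullet is in seconds and the 2.5 in minutes.

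The schedule is in Table 1 (Sections 3 and 11.2), and the Synopsis has the same table. Plateau IV has an SpO₂ range, in per cent, of "80 – 84 (target 82"). Plateau III has "85 – 89 (target 87"). Section 7.2 defines the accuracy comparison "in paired observations over a range between 80% and 100% SpO_2", and Section 17.2 accepts "SpO₂ values between 80 and 100" per cent.

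**Time.** Section 8.2 adds a second limit: "Values may be below 90% for a maximum continuous period of 3 minutes". The investigator is to enforce it with a chronograph that has a timer and an alarm. On stabilisation, Section 3 says that for each level "at least 30' will be expected in order to stabilize the" SpO₂ value (again in seconds), after which the plateau is held for 2.5 minutes. The Synopsis and Sections 7.2 and 11.2 give a plain 30 s wait instead.

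**The concern.** Section 8.2 is the exposure statement on which the risk to the volunteers is judged. They are healthy, and Section 8.1 says they gain nothing directly beyond some screening results. The statement should describe what the schedule allows, and it fails to do so in two ways.

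- It names two different lowest saturations, and the range set for the deepest plateau extends below both.
- It states a maximum duration by adding the recording time to a stabilisation time that Section 3 treats as a minimum with no upper bound.

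The practical stake is that site staff who follow Table 1 and Section 3 can find themselves outside the limits in Section 8.2, or have to choose between completing a plateau and obeying the timer. An ethics committee reading Section 8.2 alone would also take the planned exposure to be shallower, and more tightly limited in time, than the schedule makes it.

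**Working it through.** **Level.** The figures side by side:

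| Source | Figure |
|---|---|
| Section 8.2, opening sentence | lowest level 83% |
| Section 8.2, later bullet | lowest SpO₂ 82% |
| Table 1, plateau IV target | 82% |
| Table 1, plateau IV range | 80–84% |

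The 83% is printed as O₂, not SpO₂. It has to be a saturation, because the same sentence starts from 97%, the plateau I target, while inspired oxygen starts at 20.98% (Section 11.2).

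- The two Section 8.2 figures differ by 83 − 82 = 1 point, and the scheduled target equals the lower of them.
- The plateau IV floor is 82 − 80 = 2 points below the second figure and 83 − 80 = 3 points below the first.
- Of the five whole-number values in 80–84%, two (80, 81) are below 82% and three (80, 81, 82) are below 83%. This is a count of readings, not a probability.

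**Time.** First the plan's own figure: 30 s + 2.5 × 60 s = 30 + 150 = 180 s = 3 minutes. It reproduces exactly.

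Now let *s* be the stabilisation time at a plateau, so that stabilisation plus recording takes *s* + 150 s. Section 3 requires *s* ≥ 30, hence *s* + 150 ≥ 180. Under Section 3 the stated ceiling is therefore a floor. The documents give no upper bound for *s*. The values above 30 s below are assumptions for illustration only, with all stabilisation spent below 90%:

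| *s* | *s* + 150 | Excess over 180 s |
|---|---|---|
| 30 s | 180 s | 0 s |
| 45 s | 195 s | 15 s |
| 60 s | 210 s | 30 s |
| 90 s | 240 s | 60 s |

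Plateaus III (85–89%) and IV (80–84%) both lie wholly below 90%, so the limit on time below 90% applies to each:

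- if all stabilisation is below 90%, the margin at *s* = 30 is 180 − 180 = 0 s;
- if all stabilisation is at or above 90%, the margin is 180 − 150 = 30 s, and the return to 90% must fit within it.

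Sections 3 and 17.3 add a further wording: reference values are selected from at least 30 s after the plateau has stabilised. Section 8.2 counts the 30 s as the stabilisation itself. The point does not depend on this, but it leaves open when the 3-minute clock starts.

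**The case against.** The strongest reply has four parts.

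1. *The 80–84% is a measurement bin, not a permission.* Table 1 is captioned as a count of measurements, its ranges cover 80–100% in whole numbers, and the planned levels are always listed as 97, 92, 87 and 82%. The measurement-count intervals in Section 3 also stop at 82%. This is a fair reading, but it does not remove the conflict. The column is headed as the SpO₂ range, no text names 82% as a lower control limit for plateau IV, and a bin reaching 80% expects readings there. The 83% figure also conflicts with the 82% target on any reading.

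2. *Sections 7.2 and 17.2 do not describe exposure.* This stands. One is the range of the accuracy comparison. The other is a filter on computed values, which also accepts heart rates from 40 to 280 bpm. They show only that data down to 80% are anticipated.

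3. *A minimum wait and an overall maximum can coexist.* The timer would end a long plateau, and the plan tolerates fewer than 8 measurements and may enrol up to 2 additional subjects. This shows how staff might cope. It does not reconcile the passages, because Section 8.2 presents the full 2.5-minute recording as part of the 3-minute maximum and does not say that recording is cut when stabilisation runs long.

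4. *Descent and recovery cannot be judged.* Figure 1 is not shown, and detailed instructions are to be given to investigators separately. Four plateaus of 180 s use 4 × 3 = 12 of the 35 minutes, so transition time may be planned. This stands. For that reason nothing here assumes that plateaus III and IV run without a return to 90% between them.

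The 1-point gap is also smaller than the reference device's stated error of 2 digits (Section 6), but measurement error does not reconcile two printed limits.

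**Conclusion.** The concern holds. Section 8.2 gives two lowest saturations 1 point apart, and the plateau IV range reaches 2 and 3 points below them. Its 3-minute maximum is correct arithmetic only when stabilisation takes exactly 30 s, whereas Section 3 allows longer. At plateaus III and IV the margin against the limit below 90% is between 0 s and 30 s, the latter before any recovery time.

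The level finding assumes that the 83% is a saturation and that Table 1's range describes the SpO₂ values a plateau may take. The time finding assumes that Section 3's minimum means what it says. It shows a lack of margin, not that any session would exceed the cap.

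No endpoint or analysis changes. The altitude and laboratory experience cited in Section 8.2 may still support the sponsor's conclusion that residual risk is minimal. These are nevertheless safety limits applied to healthy volunteers, one of them enforced by a timer, so the conflict should be corrected and not left as a typographical matter.

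**What to change.** Reconcile Section 8.2 with Sections 3, 7.2 and 11.2, Table 1 and the matching Synopsis text so that:

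- there is one statement of the lowest saturation, and it agrees with the plateau IV range;
- the 30 s is described the same way everywhere, as a minimum or as fixed, and it is clear what it is counted from;
- the 3-minute limit is consistent with stabilisation, descent and recovery time spent below 90%.

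Then bring the risk statement and the timer instruction into line with the result. Which levels and durations are right is for the sponsor and the investigator to decide, and no value is proposed here.

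The cost is low: protocol wording and the timer instruction. No analysis has to be redone.

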9 STUDY SITES

The study will be conducted in a single Center in Italy. The list of Centers is maintained separately.

10 STUDY SUBJECTS

The study population will include adult healthy volunteers who will accept to participate in this oxygen desaturation study in a controlled clinical environment. At least 11 healthy subjects will be enrolled. Data collected on the first subject will not be used for accuracy measurements but will serve to finalize the test set up phase and ensure adequate recording procedures are used by site staff. On each of the remaining 10 subjects, 32 paired measurements will be performed in order to obtain a maximum of 320 "valid" measurements (see Section 17.2) which guarantees a statistically significant accuracy study (see point EE2.3.4 of the ISO 80601-2-61: 2017 standard).

To take into account invalid data and potential drop out samples up to 2 additional subjects may need to be enrolled. For this reason sample size for this study will be between a minimum of 11 and a maximum of 13 healthy volunteers.

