- 1) a Co-Oximeter for measuring SpO₂
- 2) an ECG for measuring cardiac frequency.

NUMBER OF SITES

Single center study conducted in Italy

EXPECTED STUDY DURATION

Around 3 weeks, from enrolment of first patient to study completion/termination of the last patient.

OBJECTIVES AND ENDPOINTS

Primary Objective:

Confirm the performance of BrOxy M in comparison with a reference, CE marked, pulse oximeter equipment in a controlled desaturation study.

Primary endpoint:

The **primary endpoint** of the study will be a comparison of the accuracy of SpO_2 and heart rate (HR) measurements obtained with BrOxy M with that obtained with the reference pulse oximeter in paired observations over a range between 80% and 100% SpO_2 .

The study will follow the procedures described in the standard ISO 80601-2-61:2017 "Medical electrical equipment - Part 2-61: particular requirements for basic safety and essential performance of pulse oximeter equipment".

Secondary Objectives:

- To assess BrOxy M performance in subjects with different skin pigmentation (Note: this is a tentative objective, since few subjects are planned to be enrolled and there is no guarantee that they will have different skin pigmentation)
- to confirm BrOxy M safety

Secondary endpoints:

The following will be verified:

- the performance of Broxy M when taking measurements on subjects with varying skin pigmentations as measured with the Fitzpatrick scale
- that no adverse events related to the use of the device, besides a temporary slight skin irritation of the wrist, will occur

SAMPLE SIZE

Based on the requirements of the standard ISO 80601-2-61:2017, at least 11 healthy subjects will be enrolled. Data collected on the first subject will not be used for accuracy measurements and will serve to finalize the test set up phase and ensure adequate recording procedures are used by site staff.

Protocol No.:

Version 1.0

Page 10 of 45

01M2020-CH.LMD

Date: 22 December 2020

To take into account invalid data and potential drop out samples up to 2 additional subjects may need to be enrolled. For this reason sample size for this study will be between a minimum of 11 and a maximum of 13 healthy volunteers.

STUDY POPULATION

The study population will include adult healthy volunteers that will accept to participate in this oxygen desaturation study in a controlled clinical environment.

INCLUSION CRITERIA

- 1. Healthy subjects of both sexes with an age \geq 18 and \leq 50.
- 2. ASA classification 1

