16 STATISTICAL ANALYSIS

16.1 OVERVIEW

Statistical analyses will be performed with SPSS, Statistical Package for the Social Sciences (SPSS Inc, Chicago, IL), by following the requirements of the standard ISO 80601-2-61:2017 ("Medical electrical equipment - Part 2-61: particular requirements for basic safety and essential performance of pulse oximeter equipment, Procedure for non-invasive laboratory testing on healthy adult volunteers).

The *significance level*, that is the probability of rejecting the null hypothesis when it is true, will be set to 0.05 (two-sided, corresponding 5% risk of concluding that a difference exists when there is no actual difference).

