16.2 ANALYSIS SETS

Analyses will regard 320 pair measurements (80 in the ambient air, and 80 for each of the four defined target levels, that will be obtained from 10 healthy subjects).

Clinical Investigational Plan			
Protocol No.:	Version 1.0	Dana 25 of 45	
01M2020-CH.LMD	Date: 22 December 2020	Page 35 of 45	

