16.3.2 Primary endpoint

The **primary endpoint** of the study regards the accuracy of SpO₂ and HR measurements of BrOxy M. The *accuracy* of the experimental BrOxy M will be evaluated by comparing SpO₂ readings of the BrOxy M to the values obtained with the secondary standard pulse oximeter equipment (Nellcor™ Bedside Respiratory Patient Monitoring System model PM1000N, Covidien LLC, USA), that is traceable to co-oximeter SaO₂ values.

The following routines will be used:

- The paired t test, to evaluate the differences between experimental and standard values: the paired sample *t*-test procedure determines whether the mean difference between two sets of observations is zero. It regards *pairs* of observations.
- Correlation analysis, to quantify the degree to which experimental and standard values are related: it is a bivariate analysis that measures the strength of the association between two variables. The degree of association is measured by a correlation coefficient (r) on a scale that varies from + 1 through 0 to 1. We expect a positive correlation: r>0.70 indicate a strong correlation, and r=1 a perfect correlation.
- Concordance correlation coefficient (CCC), to evaluate whether the experimental value is interchangeable with the standard; this statistic quantifies the agreement between a new measurement and a gold standard measurement. Also CCC varies from -1 to 1, with perfect agreement at 1.

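### Section 10 claims that 320 readings guarantee statistical significance; the design has no such property, and a significant paired t test would point to bias, not accuracy

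*Combined protocol and SAP*

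**What the plan says.** Section 10 sets the measurement plan: "On each of the remaining 10 subjects, 32 paired measurements will be performed in order to obtain a maximum of 320" valid measurements, "which guarantees a statistically significant accuracy study". It supports this with a reference to a clause of the ISO standard.

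The synopsis gives the basis for the number of subjects: "Based on the requirements of the standard ISO 80601-2-61:2017, at least 11 healthy subjects will be enrolled". The first of these is used for set-up and is not analysed. Up to 2 more may be added for invalid data or drop-out. The synopsis and Section 3 also give a minimum of 200 readings, with at least 67 in each third of the saturation range.

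Section 16.1 says that the significance level "will be set to 0.05 (two-sided, corresponding 5% risk of concluding that a difference exists when there is no actual difference". Section 16.3.2 lists five routines for the primary endpoint. The first is a paired t test, which "determines whether the mean difference between two sets of observations is zero". Section 16.2 describes the analysis set as 320 pairs "that will be obtained from 10 healthy subjects".

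The documents give no SD of the differences, effect size, power, precision target or numerical limit for acceptable agreement.

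**The concern.** The clause presents statistical significance as something the number of readings secures, and as something that speaks for the device. Neither follows.

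- **Certainty.** Whether a test is significant depends on the true bias, the spread of the differences and chance. A count cannot guarantee it, least of all a maximum count that the validity rules in Section 17.2 can reduce.
- **Direction.** The objective is to confirm performance. In the paired t test, rejection means that the mean difference from the reference is not zero. Section 16.3.2 itself says that comparable methods should have a mean difference near zero.
- **Unit.** The clause counts readings, but the readings are clustered in 10 people. Neither Section 10 nor Section 16 mentions this.

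Left in place, the clause overstates what the study can establish and gives a reader no honest statement of its precision.

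**Working it through.** **Inputs from the protocol.** 10 analysed subjects (12 if both extra subjects are added: 13 enrolled less the set-up subject); 4 plateaus with 8 readings each; two-sided 0.05; null of zero mean difference.

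**Assumptions.** The documents give neither the SD of single SpO₂ differences nor the within-subject correlation (ICC). I use SD 1, 2 and 3 points and ICC 0.1, 0.3 and 0.5, with the same correlation between any two readings on one person. The only related figure in the protocol is the reference device's error of ±2 digits (Section 6).

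**1. The plan's count.** 10 × 4 × 8 = 320, which reproduces. The minimum is 3 × 67 = 201, in line with 200. One wording slip: Section 16.2 itemises "80 in the ambient air, and 80 for each of the four defined target levels", which read literally is 80 + 4 × 80 = 400. Ambient air is itself one of the four plateaus, so 4 × 80 = 320 is evidently meant.

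**2. What significance would mean with 320 independent readings.** The paired t test rejects when the observed mean difference exceeds t(0.975, 319) × SD/√320 = 1.967 × SD/17.89. That is 0.11, 0.22 or 0.33 points for SD 1, 2 or 3.

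- If the true bias is zero, it rejects 5% of the time, whatever the number of readings.
- If the true bias is 0.3 points, it rejects with probability above 99% (SD 1), 76% (SD 2) or 43% (SD 3), by the noncentral t distribution. A noisier device is less likely to be flagged, so a non-significant result is not evidence of accuracy.

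**3. Clustering.** Design effect = 1 + 31 × ICC. Effective readings = 320 / design effect. Half-width of the 95% CI for mean bias = t(0.975, 9) × SD × √(design effect/320), with t = 2.262. The last column is the rate at which a t test on 320 pairs taken as independent rejects a true zero bias, from 10,000 simulated studies.

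| ICC | Design effect | Effective readings | Half-width, SD 1 | Half-width, SD 2 | Half-width, SD 3 | False rejection |
|---|---|---|---|---|---|---|
| 0 | 1 | 320 | 0.13 | 0.25 | 0.38 | 5% |
| 0.1 | 4.1 | 78 | 0.26 | 0.51 | 0.77 | 33% |
| 0.3 | 10.3 | 31 | 0.41 | 0.81 | 1.22 | 54% |
| 0.5 | 16.5 | 19 | 0.51 | 1.03 | 1.54 | 63% |

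For SD 2, treating all readings as independent gives 1.967 × 2/√320 = 0.22. The 0.25 in the ICC 0 row differs only because it uses 9 degrees of freedom instead of 319.

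**4. Precision from subject means.** Half-width / SD of subject mean differences = t(0.975, n − 1)/√n.

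- n = 10: 2.262/3.162 = 0.715
- n = 12: 2.201/3.464 = 0.635

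Check against step 3 at SD 2 and ICC 0.3: the SD of subject means is 2 × √(0.3 + 0.7/32) = 1.135, and 0.715 × 1.135 = 0.81, as in the table.

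**The case against.** The clause never mentions the t test. It speaks of an accuracy study and points to a clause of the standard that is not available here, so it may be a loose way of saying that 320 readings comfortably exceed the required count. The t test is one of five routines, and a significant correlation would point the other way.

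Part of this stands. The loose meaning is possible, and the point about direction is specific to the paired t test. But the minimum of 200 is already stated elsewhere, and meeting a minimum count does not guarantee significance. A significant correlation would not show agreement either.

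A reader might also draw three stronger conclusions that the documents do not support.

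- **That the clause is the only justification for the sample size.** It is not. The synopsis and Section 3 take the subject and reading counts from the standard and say what happens if the reading target is missed.
- **That the study amounts to 10 independent observations.** That is the limit as the ICC approaches 1. The documents give no ICC, and at 0.1 the effective number is 78.
- **That the plan would fail the device on a significant t test, or pass it on a non-significant one.** No section sets such a rule. Section 16.3.2 judges comparability by small differences, a mean near zero and no trend.

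**Conclusion.** The point holds as a false statement about the design, to be corrected before the plan is relied on. The count of 320 is right arithmetically but guarantees nothing: it is a maximum, it has no stated SD, power or precision behind it, and significance in the planned test of the mean difference would count against the device.

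For SpO₂ with an assumed SD of 2 points, a realistic half-width for mean bias is about 0.5 to 1.0 points over ICC 0.1 to 0.5, roughly two to five times the 0.22 implied by 320 independent readings. These figures rest on the assumed SD and ICC and on a common within-subject correlation. The multipliers 0.72 and 0.64 need neither value and apply equally to heart rate, for which no SD is assumed here.

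This does not show that the study is too small or falls short of the standard.

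**What to change.** In Section 10, keep the 10 × 32 measurement plan, the link to Section 17.2 and the reference to the standard. Delete only the guarantee clause and put in its place:

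> The number of subjects and the target of at least 200 readings follow the cited standard. With 10 to 12 analysed subjects, the 95% CI for mean bias, computed from subject mean differences, has a half-width of 0.72 to 0.64 times the SD of the subject mean differences. The number of readings alone does not determine precision, and a significant or non-significant paired t test is not a measure of accuracy.

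In Section 16.3.2, compute the confidence interval for mean bias from subject mean differences, so that the analysis matches this statement.

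The cost is wording and minor analysis work, with no added subjects, visits or procedures. The stated precision becomes less favourable.
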